7.9.3. Deaths, Serious Adverse Events, Other Significant Adverse Events

A summary table of all deaths, including reasons for deaths, will be provided. For deaths due to AE, the PT will be provided. In addition to the tabular summary, a by-patient listing of all deaths on study not attributed to study disease by the investigator will be provided.

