3.3.1. Study Rationale

Ewing's sarcoma is an aggressive sarcoma of the bone and/or soft tissue, with a peak incidence in adolescents but can occur from infancy to adulthood. A multidisciplinary approach of neoadjuvant chemotherapy, surgery, or radiation (reserved for unresectable tumors) has improved 5-year EFS and OS to 69% and 72%, respectively, in the pediatric population (Leavy et al. 2008). However, 30% to 40% of those who present initially with localized or metastatic disease will ultimately suffer a disease recurrence (Leavey et al. 2008). Time to relapse is typically short: a median of only 1.4 years for patients with initial localized disease, and 12 months for those initially metastatic (Leavey et al. 2008). The prognosis for patients after disease relapse is dismal with 5-year OS rate of only 13% and mOS of only 7 months following progression (Stahl et al. 2011; Diaz-Beveridge et al. 2015). Long-term survivors of relapsed Ewing's sarcoma are rare. There is an urgent unmet need for new therapeutic strategies to improve this dismal prognosis.

To date, salvage therapies remain inadequate and there is no single standard treatment for relapsed or refractory Ewing's sarcoma. Among the accepted regimens, although irinotecan and temozolomide have demonstrated some of the highest response rates of up to 63% and a 2-year OS rate of 36% in Ewing's sarcoma patients (Casey et al. 2009; Raciborska et al. 2013; Ju et al. 2021), these dismal outcomes highlight the need for continued improvements. Despite large multinational studies of novel combinations, treatment of relapsed Ewing's sarcoma relies entirely on chemotherapeutic agents that have been largely unchanged for decades. This highlights a need for rationale-targeted therapies beyond conventional cytotoxic chemotherapy. Based on the role of CDKs in the activation of DNA-damage signaling and repair, along with the evidence of CDK pathway aberrations in Ewing's sarcoma, it is hypothesized that the addition of abemaciclib to irinotecan plus temozolomide may be of potential benefit for treatment of Ewing's sarcoma.

Study JP04 is designed to investigate the efficacy of abemaciclib in combination with irinotecan and temozolomide for the treatment of participants with relapsed or refractory Ewing's sarcoma or Ewing's sarcoma-like tumors.

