3.7.3. Blinding

This is an open-label study. The participant, caregiver, and all staff involved in treating and caring for study participants will have full knowledge of treatment assignments.

To maintain the scientific integrity of this trial, the study team's access to aggregate safety and efficacy data will be strictly controlled prior to the interim and final analyses. Access to the electronic data capture (eDC) system will be limited to those who require this information for their role, and all access will be documented.

For the accumulated aggregate database, that is, the database to which Lilly statisticians (or those of its designee) have access, treatment assignment and other parameters that can disclose treatment assignment will be scrambled or masked. Therefore, the sponsor and all investigative sites will remain blinded to treatment group assignments for the aggregate database until the database lock for the final analysis. Scrambled treatment assignments will be used in the reporting database until the study reaches its final analysis or the study is determined to be positive by the DMC. During this time, analyses using unblinded treatment codes will be performed only at the interim analysis points specified in the protocol/SAP.

For those safety and efficacy analyses assigned to the DMC, only the designated SAC, which is independent of the sponsor, will perform analyses on unblinded data, that is, an aggregate database with correct treatment assignments.

Further details are included in the study blinding plan.

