6.1.2. Determination of Sample Size

At least 45 participants will be enrolled in the study using a 2:1 randomization ratio. The primary objective of this study is to compare the efficacy of abemaciclib in combination with irinotecan and temozolomide (Arm A) to irinotecan and temozolomide (Arm B), in terms of PFS by blinded independent review committee, in participants with relapsed or refractory Ewing's sarcoma.

Participants who are randomized but not administered treatment may be replaced to ensure that enough participants may complete the study.

Under a frequentist analysis, the study will be powered to approximately CCI assuming a PFS HR of CCI at a 1-sided alpha of CCI. This requires approximately CCI events from all randomized

participants and accounts for the futility analysis described in Section 7.12.2. However, as described in Section 7.7.1, the primary analysis will incorporate a Bayesian Augmented Control and Bayesian decision rule, altering the exact operating characteristics above. Specifying the same one-sided Type I error rate of α the Bayesian Augmented Control may increase power as high as approximately α . Section 7.7.1.6 describes the results of a simulation study to evaluate the operating characteristics of the Bayesian decision rule under varying assumptions.

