7.2. Patient Disposition

A detailed description of patient disposition will be provided. It will include a summary of the number and percentage of screened patients randomized in the study, reasons for discontinuation from study treatment, and reasons for discontinuation from the study. Reason for discontinuation from both study treatment and the study will be listed by the predetermined categories. For treatment discontinuation, these include progressive disease, AE, death, withdrawal by subject, physician decision, noncompliance with study drug, protocol deviation, study terminated by the IRB/ERB/sponsor, lost to follow-up; for study discontinuation, these include study terminated by sponsor, withdrawal by subject, lost to follow-up, death. If the reason for discontinuation is AE or death, the associated AE or cause of death will be reported. The disposition will also be listed. All patients randomized in the study will be included in the summaries and listings.

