7.9. Safety Analyses

Safety analyses will be based on the safety population, unless otherwise stated, and summarized by treatment arm corresponding to the actual regimen received at first dose.

Safety analyses will be completed as specified below, unless COVID-19 impact creates a situation requiring a change to an existing analysis or a need for additional analyses as outlined by Nilsson et al. (2020).

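### SAP 7.9.3 does not split deaths by time from last dose and lists only those not attributed to disease, so early all-cause deaths are not tabulated separately by arm

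*SAP*

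**What the plan says.** SAP 7.9.3 plans two outputs. The first is a table: "A summary table of all deaths, including reasons for deaths, will be provided". Under SAP 7.9, safety results are "summarized by treatment arm corresponding to the actual regimen received at first dose", so the table is by arm. The second is a listing: "a by-patient listing of all deaths on study not attributed to study disease by the investigator will be provided". Neither mentions time since last dose.

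The listing turns on the investigator's view of the cause of death. The trial is open label (Protocol 3.7.3): "The participant, caregiver, and all staff involved in treating and caring for study participants will have full knowledge of treatment assignments".

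SAP 7.9.2 does contain a treatment window. It counts an adverse event as treatment-emergent if it starts on or after first dose and no later than 30 days after treatment ends, or at any later time if it is serious and related. That window governs the onset of adverse events. It is not applied to deaths.

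Deaths appear in other planned outputs too. SAP 7.2 summarizes reasons for leaving treatment and reasons for leaving the study, with death a category in both. It states: "If the reason for discontinuation is AE or death, the associated AE or cause of death will be reported". Disposition is also listed for everyone randomized. SAP 7.9.2 summarizes serious events and treatment stopped because of an adverse event or death. SAP 7.7.2 plans Kaplan-Meier curves for overall survival.

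**The concern.** Deaths are a named part of the secondary safety endpoint (Protocol 3.4, SAP 5). Protocol 3.3.3 names overlapping risks of the triplet, including low counts, febrile neutropenia, liver toxicity and pneumonitis. The safety question is whether adding abemaciclib brings more deaths during treatment or shortly after it.

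Whole-study death totals answer that poorly here. The protocol describes the outlook after relapse as a "5-year OS rate of only 13% and mOS of only 7 months following progression". Survival follow-up runs to death, withdrawal or study completion. Most participants in both arms may therefore die in follow-up, and the totals then converge whatever happened early.

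The listing does not fully repair this. An early death in a participant with advancing tumor can be put down to disease, which removes it from the 7.9.3 listing. That judgment is made with the arm known, so it could differ between arms.

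**Working it through.** **Plan's own figures.** Section 7.9.3 states none. The power, hazard ratio, alpha and event count in SAP 6.1.2 are blacked out and are not needed here.

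**Step 1. Trace an early death through the planned outputs.** Take a participant who stops treatment for progression or an adverse event and dies 15 days later, with the death attributed to disease.

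| Output | Does this death appear? | Is it separated by time from last dose? |
|---|---|---|
| 7.9.3 table | Yes, with reason | No, pooled with all later deaths |
| 7.9.3 listing | No, because of the attribution | Not applicable |
| 7.2 and 7.9.2, treatment stopped because of death | No, treatment stopped for another reason | Not applicable |
| 7.2, study discontinuation and disposition listing | Yes, with cause | No split stated; the listing is not said to show days from last dose |
| 7.9.2, adverse events | Only if an adverse event was recorded; expected progression is not one unless worse than expected (Protocol Attachment 10) | The window applies to event onset, not date of death |
| 7.7.2, overall survival | Yes, all causes | No, timed from randomization and analyzed as randomized |

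The death appears in several places, but no output counts it by arm as an early death.

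**Step 2. Arm sizes.** SAP 6.1.2: "At least 45 participants will be enrolled in the study using a 2:1 randomization ratio". At 45, this gives 45 × 2/3 = 30 in Arm A and 45 × 1/3 = 15 in Arm B.

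**Step 3. How far totals converge.** Assume exponential survival with median *m* months and 24 months of follow-up. The lower value, *m* = 7, is the protocol's figure after progression. The upper value, *m* = 12, and the 24 months are assumptions. The proportion dead is 1 − 2^(−24/*m*).
- *m* = 7: 0.907, or 27.2 of 30 and 13.6 of 15.
- *m* = 12: 0.750, or 22.5 of 30 and 11.25 of 15.

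Suppose two extra early deaths occur in Arm A among people who would otherwise have had those chances of dying by 24 months. They add 2 × (1 − 0.907) = 0.19 to 2 × (1 − 0.750) = 0.50 deaths to the total.

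**Step 4. What a split would show.** The counts are assumed, with 30 and 15 participants; *p* is Fisher's exact two-sided.

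| Early deaths, A vs B | Whole-study deaths, A vs B | *p*, early | *p*, total |
|---|---|---|---|
| 3/30 vs 0/15 (10.0% vs 0%) | 20/30 vs 10/15 (66.7% each) | 0.54 | 1.0 |
| 5/30 vs 0/15 (16.7% vs 0%) | 20/30 vs 10/15 (66.7% each) | 0.153 | 1.0 |
| 6/30 vs 1/15 (20.0% vs 6.7%) | 24/30 vs 12/15 (80% each) | 0.395 | 1.0 |

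**Step 5. Limits of the split.** If the true early-death rate in Arm B is 5%, 10% or 20%, the chance of seeing none among 15 is (1 − rate)^15 = 46%, 21% or 3.5%. With no treatment effect, two early deaths both fall in Arm A with probability (30 × 29)/(45 × 44) = 870/1980 = 44%.

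**The case against.** The strongest reply is that most of these deaths are already visible. SAP 7.2 covers leaving the study as well as leaving treatment. A participant who stops for progression and dies two weeks later would have death as the reason for leaving the study, with its cause reported and the disposition listed, whatever the attribution. Attributing a death to disease does not erase a recorded sepsis or liver failure, which remains a treatment-emergent event if it began in the window, related or not. Survival curves carry no attribution filter, so a clear early excess in Arm A should show. An independent committee reviews safety at least about every six months (SAP 7.12.1).

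All of that stands. From 7.9.3 alone, a reader might infer that the plan has only one death listing and that an early excess in Arm A would go unseen. The documents support neither inference, for the reasons just given.

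Two further points stand. Numbers this small cannot support a test, as Steps 4 and 5 show. Protocol 3.10.3.2 also refers safety analysis to CAMPFIRE Master Protocol Section 10.3.1 as well as the SAP. That section was not available and may already require a split.

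The reply does not supply an arm-by-arm count of all-cause deaths on treatment or within 30 days of last dose. Disposition has no stated timing split, the adverse-event tables depend on whether the event was judged expected progression, and survival is not tied to exposure.

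**Conclusion.** The concern holds as a limited gap in safety reporting. On the documents supplied, no planned output tabulates by arm all-cause deaths on treatment or within 30 days of last dose, and the 7.9.3 listing is selected on open-label attribution. The deaths most affected are those soon after treatment stopped for another reason and attributed to disease.

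The size can only be illustrated. Under the assumed 7 to 12 month median and 24 months of follow-up, two extra early deaths in Arm A move its total by 0.2 to 0.5 of a death. An assumed 5/30 versus 0/15 can sit inside equal totals. These are examples, not forecasts. A windowed table would be descriptive, and nothing here affects the primary analysis. The conclusion is subject to Master Protocol Section 10.3.1.

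**What to change.** First check CAMPFIRE Master Protocol Section 10.3.1 for an existing split. If there is none, amend SAP 7.9.3 as follows.

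- Split the death table by arm into (1) deaths on treatment or within 30 days of last dose and (2) later deaths, with reasons in each part.
- List every death in part (1) regardless of attribution, with days since last dose, reason for death and adverse events ongoing at death.
- Keep the existing listing of deaths not attributed to disease for part (2).
- State the anchor as the last dose of any study drug, since Protocol 3.7.8.2 allows drugs to be stopped separately, and align it with the 30-day window of 7.9.2, which is worded from treatment discontinuation.
- Label the output as descriptive.

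The cost is SAP wording, one table split and a longer listing. Survival information and dosing are already recorded, so no new collection or change in conduct should be needed. The downside is that the early listing will include some deaths that truly were due to disease.

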7.9.4. Clinical Laboratory Evaluation

All relevant hematology and chemistry laboratory values will be graded according to CTCAE version 5. These calculated grades will be summarized by maximum postbaseline grade over the entire study for each treatment arm. Treatment-emergent changes will be summarized by the

maximum postbaseline grade, and a shift table of baseline grade by maximum postbaseline grade will be produced.

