Height, weight, and BSA	X			X			X			X			X			
-7 days is acceptableBSA must be calculated with Mosteller formula (see also Attachment 6)
Vital signs ^a	See Notes															
Temperature, blood pressure, pulse rate, and respiratory ratePerform D1-5 of every cycle
Perform before irinotecan infusion and within 1 hour after each irinotecan infusionNote: If not administering irinotecan (i.e., due to a dose hold), only Day 1 vitals are required
Physical examination	X			X			X ^a			X ^a			X ^a			
Complete before treatment administrationInclude respiratory auscultation
CCI	X			X			X			X			X			CCI

Procedure	All Treatment Periods (Cycle = 21 Days)															Notes
	Cycle 1			Cycle 2			Cycle 3			Cycle 4			Cycle 5-n			
Relative Day within Dosing Cycle	1	8	15	1	8	15	1	8	15	1	8	15	1	8	15	

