
Procedure	All Treatment Periods (Cycle = 21 Days)															Notes
	Cycle 1			Cycle 2			Cycle 3			Cycle 4			Cycle 5-n			
Relative Day within Dosing Cycle	1	8	15	1	8	15	1	8	15	1	8	15	1	8	15	
Participant abemaciclib dosing diary	X	X	X	X	X	X	X	X	X							
Provide to participants on C1D1, C2D1 and C3D1Participants/caregiver should complete daily through Cycle 3 Day 21Review diary at each study visit through C4D1 for the date and time of each dose (±3 days is acceptable for review)
Hematology ^b	X	X	X	X	X	X	X	X	X	X	X	X	X	X	X	
See Attachment 2 for sample collection guidanceD1, D8, and D15 of all cyclesCollect ≤3 days before starting a new cycle of therapy (i.e., Day 1). If not starting a new therapy (i.e., Days 8 and 15), a window ±3 days is acceptable.May collect more frequently if indicated.After Cycle 3, Days 8 and/or 15 CBCs may be eliminated if irinotecan has been discontinued at investigator’s discretion
Clinical chemistry ^b	X	X	X	X	X	X	X	X	X	X	X	X	X	X	X	
See Attachment 2 for sample collection guidanceD1, D8, and D15 for all cyclesCollect ≤3 days before starting a new cycle of therapy (i.e., Day 1). If not starting a new therapy (i.e., Days 8 and 15), a window ±3 days is acceptable. May collect more frequently if indicated.After Cycle 3, Days 8 and/or 15 clinical chemistry may be eliminated at investigator’s discretion.

Procedure	All Treatment Periods (Cycle = 21 Days)															Notes	
	Cycle 1			Cycle 2			Cycle 3			Cycle 4			Cycle 5-n				
Relative Day within Dosing Cycle	1	8	15	1	8	15	1	8	15	1	8	15	1	8	15		
Urine and serum pregnancy test ^b	X			X			X			X			X			
Only females of childbearing potentialSee Attachment 2 for sample collection guidancePerform at start of each cycle (≤3 days) or as required per local regulations and/or institutional guidelinesSerum confirmation only needed if urine test is positive	
Drug product acceptability and palatability questionnaire	X			X			X	See Notes									
For Arm A participants onlyFor Day 1 of Cycles 1-3 (+3 days acceptable as long as participant is on-site), perform within approximately 30 minutes after doseIf the method of abemaciclib administration changes at any point during the trial, the questionnaire corresponding to the new administration method should be completed at the next clinic visitSee Section 3.9.1.1

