3.7.8.2. Discontinuation of One Study Treatment

Participants may discontinue irinotecan and/or temozolomide (due to chemotherapy-associated toxicities) while continuing abemaciclib upon discussion with the Lilly CRP/CRS. If abemaciclib must be discontinued, participants may continue to receive irinotecan and/or temozolomide. For all study drugs, if dose reductions are required beyond the lowest dose, the drug should be discontinued. Continuation on chemotherapy beyond Cycle 12 will be up to the investigator's discretion and the individual participant's situation. Prior to continuing the participant on chemotherapy beyond Cycle 12, the investigator should discuss with the Lilly CRP/CRS. Abemaciclib may continue beyond Cycle 12 until discontinuation criteria is met.

Dose Modification for Neutropenia						
Note: For hematologic toxicities, dose holds, and reductions - apply simultaneously to all drugs as indicated						
	Abemaciclib		Irinotecan		Temozolomide	
Severity and Duration	Dose Hold	Dose Reduction	Dose Hold	Dose Reduction	Dose Hold	Dose Reduction
Grade 3	Recommend G-CSF in subsequent cycle					
Grade 4 Initial incident	Hold until ANC CCI	Consider 1 dose level reduction. If already taking G-CSF, reduce 1 dose level.	Hold until ANC CCI	Reduce 1 dose level	Hold until ANC CCI	No reduction Recommend G-CSF in subsequent cycle
Grade 4 >7 days duration or >14-day cycle delay		Reduce 1 dose level Recommend G-CSF in subsequent cycle		Recommend G-CSF in subsequent cycle		Reduce 1 dose level Recommend G-CSF in subsequent cycle
Grade 4 Recurrent ^a						Reduce 1 dose level Recommend G-CSF in subsequent cycle
Dose Modification for Febrile Neutropenia						
Note: For hematologic toxicities, dose holds, and reductions - apply simultaneously to all drugs as indicated						
Grade 3 Initial incident	Hold until resolution	Consider 1 dose level reduction Recommend G-CSF in subsequent cycle	Hold until resolution	Consider 1 dose level reduction Recommend G-CSF in subsequent cycle	No change	
Grade 3 Recurrent ^a				Reduce 1 dose level Recommend G-CSF in subsequent cycle		
Grade 4				Reduce 1 dose level Recommend G-CSF in subsequent cycle		Reduce 1 dose level if not previously on G-CSF Reduce 2 dose levels if G-CSF was used Recommend G-CSF in subsequent cycle

Abbreviations: ANC = absolute neutrophil count; G-CSF = granulocyte-colony stimulating factor.

Grade 3: ANC < 1000/mm³; **Grade 4:** ANC < 500/mm³.

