7.9.5. Vital Signs and Other Physical Findings

Temperature, blood pressure, pulse rate, weight, BSA, and Lansky/Karnofsky Performance Status will be summarized by cycle, including a summary of treatment-emergent abnormal changes.

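### Whole-study worst-grade laboratory tables (SAP 7.9.4) depend partly on number of draws and time on treatment, which may differ by arm; a Cycles 1-3 table should be added

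*SAP*

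**What the plan says.** **How laboratory results are summarized.** SAP 7.9.4 grades hematology and chemistry by CTCAE and states: "These calculated grades will be summarized by maximum postbaseline grade over the entire study for each treatment arm". It adds a shift table from baseline grade to that same maximum. It defines no common observation window, no count of assessments and no adjustment for exposure. SAP 7.9.1 tabulates cycles received and duration on therapy, but separately from the laboratory tables.

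**How often blood is drawn.** Protocol Table JP04.2 (Section 3.2) schedules hematology and chemistry on Days 1, 8 and 15 of every cycle, then relaxes this:
- Chemistry: "After Cycle 3, Days 8 and/or 15 clinical chemistry may be eliminated at" the investigator's discretion, with no treatment condition.
- Hematology: "After Cycle 3, Days 8 and/or 15 CBCs may be eliminated if irinotecan has been discontinued", again at the investigator's discretion.
- Both: "May collect more frequently if indicated".

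**Who can be on treatment without irinotecan.** Under Protocol 3.7.8.2, participants may stop irinotecan and/or temozolomide for toxicity while continuing abemaciclib. Chemotherapy past Cycle 12 is discretionary, whereas "Abemaciclib may continue beyond Cycle 12 until discontinuation criteria is met". Protocol 3.7.3 confirms that treating staff know the assignment.

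**The concern.** A maximum over all postbaseline samples can only rise as samples are added. If two participants have the same underlying toxicity, the one sampled more often, or for longer, is more likely to show a high grade. The plan allows both quantities to vary after Cycle 3, and one source of variation is structural: a participant who has stopped both chemotherapy drugs can still be on study drug only in Arm A. In that setting Day 8/15 blood counts may be dropped while treatment continues, and total time on treatment may also be longer.

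Laboratory abnormalities are a named component of the secondary safety endpoint. Neutropenia and AST/ALT increases are adverse events of special interest for abemaciclib (Protocol 3.9.2.1). A by-arm worst-grade table will be read as showing what abemaciclib adds. As specified, it could show or hide a difference that comes from sampling, and the reader would have no assessment counts with which to judge.

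**Working it through.** The documents give no figure for this point, so there is none to reproduce. The draw counts below follow from the schedule. The probabilities rest on assumed risks.

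**1. Scheduled draws per participant over n cycles** (Table JP04.2)
- Full schedule: 3n.
- Chemistry with both Day 8 and Day 15 dropped after Cycle 3: 9 + (n − 3).
- n = 8: 3 × 8 = 24 versus 9 + 5 = 14.
- n = 12: 3 × 12 = 36 versus 9 + 9 = 18.

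These counts include Cycle 1 Day 1, which will usually serve as baseline under SAP 7.1.2, so postbaseline counts are one lower on each side. For hematology the reduced counts are a limiting case, reached only if irinotecan has stopped by the end of Cycle 3. A participant still on irinotecan keeps the full schedule.

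**2. Effect on the worst-grade measure**

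Assume independent draws, with Grade 3+ probability q at each Day 8 or 15 draw and r × q at each Day 1 draw. Cycle-start criteria favor recovered values on Day 1, but a failing Day 1 sample still counts toward the maximum. The criteria themselves are not visible, so r is set to 0, 0.5 and 1.
- P(full) = 1 − [(1 − q)²(1 − rq)]ⁿ
- P(reduced) = 1 − [(1 − q)²(1 − rq)]³ × (1 − rq)ⁿ⁻³
- If half of one arm is reduced and the other arm is fully sampled, with equal true risk and equal duration, the arm difference is 0.5 × [P(full) − P(reduced)].

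Example with n = 8, q = 0.05, r = 0.5. Per cycle, 0.95² × 0.975 = 0.880. P(full) = 1 − 0.880⁸ = 64.1%. P(reduced) = 1 − 0.880³ × 0.975⁵ = 40.0%. The arm difference is 0.5 × 24.1 = 12.0 points.

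Results for n = 8:

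| q | r | Full schedule | Reduced schedule | Arm difference (points) |
|---|---|---|---|---|
| 0.01 | 0 | 14.9% | 5.9% | 4.5 |
| 0.01 | 0.5 | 18.2% | 9.6% | 4.3 |
| 0.01 | 1 | 21.4% | 13.1% | 4.2 |
| 0.03 | 0 | 38.6% | 16.7% | 10.9 |
| 0.03 | 0.5 | 45.6% | 26.2% | 9.7 |
| 0.03 | 1 | 51.9% | 34.7% | 8.6 |
| 0.05 | 0 | 56.0% | 26.5% | 14.7 |
| 0.05 | 0.5 | 64.1% | 40.0% | 12.0 |
| 0.05 | 1 | 70.8% | 51.2% | 9.8 |
| 0.10 | 0 | 81.5% | 46.9% | 17.3 |
| 0.10 | 0.5 | 87.7% | 64.7% | 11.5 |
| 0.10 | 1 | 92.0% | 77.1% | 7.5 |

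The range is about 4 to 17 points. At least 45 participants randomized 2:1 gives about 30 and 15, so one control participant is 1/15 = 6.7 points. The range therefore corresponds to about 0.6 (4.2/6.7) to 2.6 (17.3/6.7) control participants. If the same fraction were reduced in both arms, the difference at equal duration would be zero.

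**3. Duration alone**

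With full sampling in both arms, q = 0.03 and r = 0.5, 6 versus 4 cycles gives 36.6% versus 26.2%, and 12 versus 6 cycles gives 59.8% versus 36.6%. Longer treatment raises the recorded rate and thinner sampling lowers it, so the net direction for Arm A cannot be stated in advance.

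**The case against.** The case against is substantial.

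- **No imbalance is shown.** The permissions read the same for both arms, both arms have the full schedule through Cycle 3, and extra draws are allowed. This stands: a distortion is possible, not demonstrated.
- **The illustration is generous.** Constant, independent risk ignores correlation within a participant and the dose holds, reductions and discontinuations that follow toxicity. The figures probably overstate the effect. They show a mechanism and are not a forecast.
- **The table is descriptive.** SAP 7.9.4 plans no formal test, and worst grade ever seen is a legitimate summary. That is a reason to keep the table, but a by-arm display will still be compared across arms.
- **Some context exists.** Exposure is summarized, and liver abnormalities trigger repeat testing (Protocol 3.9.3.1.1). Neither gives the number of laboratory assessments, and repeat testing begins only after an abnormal sample has been taken.

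Three stronger readings are tempting but not supported:

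- **Vital signs have the same defect.** Required readings do fall when irinotecan is not given ("If not administering irinotecan (i.e., due to a dose hold), only Day 1 vitals are required"), but SAP 7.9.5 says these measures "will be summarized by cycle, including a summary of treatment-emergent abnormal changes". The whole-study worst-grade rule does not apply to them, and post-infusion readings lapse because there is no infusion.
- **Safety rates in general are distorted.** Adverse events are collected continuously, and the treatment-emergent event tables do not use this rule. The point concerns laboratory-abnormality rates.
- **The full-versus-reduced columns are arm differences.** They compare one fully sampled participant with one fully reduced participant. An arm difference requires unequal use of the reduction, unequal duration, or both.

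**Conclusion.** The point holds for the laboratory tables. Whole-study maximum-grade rates for hematology and chemistry depend partly on the number of draws and the time on treatment. After Cycle 3 the protocol lets both vary, with an asymmetry available only to Arm A. The schedule counts (24 versus 14, and 36 versus 18) are exact for chemistry when both mid-cycle draws are dropped. The spurious difference of roughly 4 to 17 points rests on assumed per-draw risks of 1% to 10%, independent draws, 8 cycles, and half of one arm reduced against none of the other. Actual size and direction are unknown. That argues for prespecifying a comparison on a common schedule, because a reader could not correct the whole-study table afterwards. Neither the primary analysis nor the adverse event tables are affected by this rule.

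**What to change.** In SAP 7.9.4:

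1. Add a maximum-grade table and a baseline-shift table restricted to Cycles 1-3, where both arms have the same scheduled Day 1/8/15 sampling. Name these as the main between-arm laboratory comparison. Define the window exactly, including whether the Cycle 4 Day 1 pre-cycle sample belongs to it and how unscheduled draws are counted.
2. Keep the whole-study maximum-grade and shift tables as descriptive, showing the number of laboratory assessments and person-time per arm.

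The blood-draw schedule need not change. The cost is a paragraph of SAP text and one or two extra tables, settled before database lock. The restricted tables do not cover late toxicity, which the whole-study tables still show. Participants who stop before the end of Cycle 3 will still contribute fewer draws, so the comparison is on a common schedule rather than on perfectly equal sampling.
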